4.1.1.2 Sampling for participant interviews

At point of consent to the main trial, participants will indicate their interest in taking part in the interview study. Their details will be passed to the process evaluation researcher who will use demographic information (age, sex, ethnicity), to generate a sampling matrix to create a pool of participants that will be used to select a sample. The aim is to select a sample which is inclusive of people from different backgrounds to represent and learn about a range of experiences. The researcher will contact them to reconsent for interview. If we receive a large response to our invitation, not everyone will be invited for interview; this will be explained to participants.

4.1.1.3 Healthcare practitioner interviews

We will interview approximately 10 healthcare practitioners to explore and understand their experiences of recruitment; understand more about the care pathways at different sites; and explore perceived facilitators and barriers to delivering the interventions as per protocol. Interviews will be arranged shortly after a site has opened to recruitment and carried out in the same way as described above. A second interview may be required for some healthcare practitioners, after a higher proportion of participants have been randomised, to further explore how inserts are being prescribed and identify any additional training or support needs.

4.1.1.4 Non-participant interviews

Semi-structured interviews will be conducted by telephone or Microsoft Teams of people who were eligible to participate in the trial but declined to do so. These interviews will seek to understand their decision not to participate. Informed consent will be confirmed verbally prior to each interview. Interviews will be audio digitally recorded on an encrypted recorder or via Teams, anonymised, and transcribed verbatim.

Quantitative and qualitative data from the internal pilot process evaluation will be analysed continuously and reported to the Trial Management Group regularly so appropriate actions can be discussed. Adaptations to recruitment and intervention delivery processes will be implemented ahead of the main trial.

4.2 Main trial interviews

A larger sample of participant (n=24) and healthcare practitioner (n=15) interviews will be conducted to gain a greater understanding of the experiences of those taking part in the main trial.

4.2.1 Participant interviews

To ensure maximum variation, purposive sampling will be used to identify and invite 24 randomised participants from across different sites to take part in an interview based on age, sex, socioeconomic and working status. Interviews will take place after three months of intervention use. We will then seek to repeat these interviews after six months to explore acceptability, adherence, and intervention fidelity.

All interviews will be arranged and conducted in the same way as the internal pilot interviews (see section 4.3.1)

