2.7.2 Objectives

- i) To undertake an internal pilot to test and refine trial procedures, and establish screening recruitment processes in secondary and community care;
- ii) Review internal pilot data and recruitment optimisation findings, adapt procedures accordingly prior to rollout to main trial;
- iii) Run a definitive multicentre parallel group, blinded RCT recruiting 438 participants from up to 25 UK centres;
- iv) To conduct a mixed-methods, embedded process evaluation to inform trial recruitment and insole device adherence, reasons for non-adherence;

v) To evaluate the cost-effectiveness of shoe stiffening inserts compared to sham inserts over 12 months follow-up.

3. Trial Design

A multicentre, parallel group, participant-blinded, sham-controlled RCT with internal pilot and embedded process evaluation and economic evaluation.

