4.1.1 Methods

4.1.1.1 Participant interviews

We will interview six participants from six different sites to explore their reasons for, and expectations of taking part in the trial; experience of recruitment into the trial; and experiences of wearing their prescribed inserts and strategies for increasing usage/promoting adherence.

Interviews will be conducted approximately 12-weeks after randomisation. Participants may also be invited to a second interview later in the pilot phase to explore ongoing adherence. Semi-structured interviews will be conducted by telephone or Microsoft Teams. Informed consent will be confirmed verbally prior to each interview. Interviews will be audio digitally recorded on an encrypted recorder or via Teams, anonymised, and transcribed verbatim.

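### The main-trial interviews, which are meant to explore reasons for non-adherence, are timed by insert use and sampled without adherence, so people who stopped early may be few or absent

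*Protocol*

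**What the plan says.** Objective iv (protocol section 2.7.2) is "To conduct a mixed-methods, embedded process evaluation to inform trial recruitment and insole device adherence, reasons for non-adherence". Section 3.12 collects adherence and reasons for non-adherence by questionnaire, then names the section 4.2 interviews as the place where they are explored in more depth.

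On who is interviewed, section 4.2.1 states that "purposive sampling will be used to identify and invite 24 randomised participants from across different sites", the selection "take part in an interview based on age, sex, socioeconomic and working status". On when, it states "Interviews will take place after three months of intervention use". On the second round, it states "We will then seek to repeat these interviews after six months to explore acceptability, adherence, and intervention fidelity".

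The internal pilot counts time differently. Section 4.1.1.1 states "Interviews will be conducted approximately 12-weeks after randomisation".

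Three other places bear on the point. Section 3.5.3 lists adherence and reasons for non-adherence as a secondary outcome. Table 2 schedules adherence at months 1, 3, 6 and 12. Section 3.10.1 keeps people who stop wearing the inserts in follow-up.

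**The concern.** The interviews have to reach people who gave up on the inserts or hardly wore them, because those are the people who can explain non-adherence. Section 4.2.1 does not secure this. Its timing depends on accumulated use, and someone who stops after two weeks never accumulates three months of use. Its sampling aims for maximum variation, but the listed factors leave out the characteristic that the interviews are meant to explore. The six-month round goes back to the same people, so it cannot bring in anyone missed at three months.

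What is at stake is interpretation. The primary outcome is at three months, so stopping before then is the non-adherence most likely to dilute the intention-to-treat difference. Section 4.3 says that the qualitative data will help to explain the main findings, and section 8.4.6 foresees per-protocol or complier-average analyses. If the trial shows little or no effect, interviews drawn mostly from continuing wearers would say little about why others stopped.

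**Working it through.** **1. The texts side by side**

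| Item | Pilot (4.1.1.1, 4.1.1.2) | Main trial (4.2.1) |
|---|---|---|
| Number of participants | 6 | 24 |
| Clock starts at | randomisation | insert use |
| Time | about 12 weeks | three months |
| Sampling factors | age, sex, ethnicity | age, sex, socioeconomic and working status, across sites |
| Adherence a stated factor | no | no |

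The two clocks agree for someone who wears the inserts throughout. They part for someone who stops early: that person reaches 12 weeks after randomisation but not three months of use. Section 4.2.1 also says that interviews are arranged as in the pilot, but it sets its own timing, and the section it points to (4.3.1) is not in the protocol. The cross-reference therefore does not settle the question.

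**2. Could adherence be used for sampling?** Yes. By the time of the interviews, adherence has been scheduled at month 1 and month 3 (Table 2), and people who stopped are still in follow-up (section 3.10.1). No new data are needed.

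**3. How many stoppers would 24 interviews contain?** The protocol states no figure to reproduce and no stopping rate, so the rate p is an assumption, shown over a range. If the 24 are treated as drawn without regard to adherence, the number of stoppers is Binomial(24, p):

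- expected number = 24 × p
- chance of none = (1 − p)^24
- chance of exactly one = 24 × p × (1 − p)^23

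Worked at p = 10%: expected 24 × 0.10 = 2.4; chance of none 0.9^24 = 0.080; chance of exactly one 24 × 0.10 × 0.9^23 = 0.213; chance of none or one 0.080 + 0.213 = 0.29.

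| Assumed rate of stopping by three months | Expected among 24 | Chance of none | Chance of at least three |
|---|---|---|---|
| 5% | 1.2 | 29.2% | 11.6% |
| 10% | 2.4 | 8.0% | 43.6% |
| 20% | 4.8 | 0.5% | 88.5% |
| 30% | 7.2 | below 0.1% | 98.8% |

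The result depends heavily on the assumed rate. At 5% to 10% the interviews may well hold too few stoppers to support a theme. At 20% or more, chance alone would usually supply several. Purposive selection is not a random draw, so the table only shows the order of magnitude.

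**The case against.** The strongest reply is that section 4.2.1 excludes nobody. Its frame is randomised participants, and the sentence on three months describes timing, not eligibility. It can be read as three months after the inserts were supplied, which fits the role that section 3.12 gives these interviews. This stands. A reader might infer that none of the 24 could be an early stopper, but that follows only if the timing phrase is taken as an entry condition, and only for people who stopped before three months.

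A reader might also infer that people who stopped drop out of the process evaluation altogether, so that objective iv cannot be met. The protocol does not support that. The evaluation is mixed-methods, people who stop remain in follow-up, and reasons for non-adherence are collected by questionnaire. Six pilot interviews are timed from randomisation and cover the experience of wearing the inserts.

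Nor is non-adherence the same as early stopping. Section 3.12 defines adherence as a proportion of possible footwear use, so a low user can reach three months of use even on the literal reading. Someone interviewed at three months who stops before six can be heard in the second round.

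Finally, a fixed quota of non-adherent interviewees is one qualitative design among several, and nothing in the protocol yields a particular number. This also stands.

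These replies leave two things unanswered: the timing phrase is ambiguous and differs from the pilot's, and no sampling factor ensures that early stoppers are interviewed.

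**Conclusion.** The point holds in a limited form. The interviews that section 3.12 names for in-depth work on non-adherence are timed by an ambiguous phrase and sampled on factors that omit adherence. They may therefore include few early stoppers, or none on a literal reading. The size cannot be fixed from the protocol: it runs from about one expected stopper among 24 at an assumed 5% rate to about five at 20%, on the simplification that selection is unrelated to adherence.

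The consequence is confined to one component of the process evaluation and to its use in explaining the trial result. The primary outcome, its analysis, the sample size, power and type I error are not affected. It is worth correcting because the correction costs almost nothing.

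**What to change.** In section 4.2.1:

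- State that the first main-trial interviews take place about three months after randomisation, whether or not the participant still wears the inserts.
- Add adherence or discontinuation status, taken from the month-1 and month-3 questionnaires, to the purposive sampling factors, so that people who stopped or used the inserts little are deliberately included.
- Keep 24 participants, and leave any minimum number of stoppers or low users to the qualitative team.
- Correct the cross-reference to section 4.3.1.

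The cost is protocol wording only, with no extra interviews and no new data items. One small drawback is that people who stopped may be harder to recruit for interview, which is itself a reason to plan for them.

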4.2.2 Healthcare practitioner interviews

A sampling matrix will be used to select a purposive sample of up to 15 healthcare practitioners based on their different backgrounds and places of work e.g., community or secondary care. Staff will be invited to a one-on-one online interview or to join an online focus group. The aim will be to understand as much as possible about intervention delivery and fidelity but also to assess the impact of any adapted processes or procedures introduced because of pilot study findings.

4.3 Analysis and reporting

All qualitative data from both the pilot and main phase of the trial will be analysed using the framework method proposed by Ritchie and Spencer.[38] The framework analysis will compare and interpret the data from participants at different stages over the trial and separate frameworks will be constructed for participant and healthcare practitioner responses to enable comparison. These data will be used to aid interpretation and explanation of the main trial findings.

The software package NVivo will be used to manage the data and facilitate this process. Researcher bias will be minimised through regular crosschecking of the data and findings by the members of the research team. Quotes will be used as exemplars of key themes.

Coded interviews, observations and a full record of issues raised will be discussed in detail at the TMG and summarised for the oversight committees. Good practice at sites will be shared with other recruiting sites.

5. Ethical considerations

The trial will be conducted in full conformance with the principles of the Declaration of Helsinki and to Good Clinical Practice (GCP) guidelines. It will also comply with all applicable UK legislation and Warwick Standard Operating Procedures (SOPs). All data will be stored securely and held in accordance with Data Protection Act 2018 & UK GDPR.

All required ethical approvals for the trial will be sought using the Integrated Research Application System (IRAS). We do not foresee any substantial ethical issues as the PPI interactions have been very positive about the trial and our trial team are experienced in preparing similar applications.

The Chief Investigator will ensure that this study is conducted in full conformity with relevant regulations and with the ICH Guidelines for Good Clinical Practice (CPMP/ICH/135/95) June 2017. Before enrolling patients into the trial, each site must ensure that the local conduct of the trial has the agreement of the relevant NHS Trust Research & Development (R&D) department. Sites will not be permitted to enrol patients until the R&D department has confirmed Capability and Capacity and a site agreement is in place.

Trial staff will ensure that participants' anonymity is maintained. The participants will be identified by an ID number on all Case Report Forms (CRF), participant questionnaires and electronic database. Data will be entered into a secure online trial database provided by WCTU. Paper-based CRFs will be stored on site at WCTU under locked, secure conditions for the duration of the trial.

Direct access to source data and documents will be granted to authorised representatives from the sponsor, sites and regulatory authorities to permit trial related monitoring, audits and inspections.

6. Adverse Event Management

6.1 Definitions

6.1.1 Adverse events (AE)

An adverse event (AE) is defined as any untoward medical occurrence in a clinical trial participant which does not necessarily have a causal relationship with the research.

An adverse device effect (ADE) is an adverse event related to the use of an investigational medical device, such as an insert. This includes any adverse event resulting from insufficiencies or inadequacies in the instructions for use, the deployment, the installation, the operation, or any malfunction of the investigational medical device (active or sham shoe inserts). This also includes any event that is a result of a user error or intentional misuse. For the purposes of the BigTOE trial, ADEs will be considered as AEs and recorded accordingly.

All AEs will be collected from the point of randomisation onwards, up to 12 months. Events occurring before randomisation will not be recorded.

Some events which occur during treatment (use of the inserts) will be considered normal outcomes from when using shoe inserts and will not be recorded as adverse events nor reported as a serious adverse event, unless in the opinion of the clinical team, they are considered untoward, excessive, or outside of what might normally be expected for insert use. These are events that are excluded from AE/SAE recording and reporting, this is not to be confused with known SAEs that are to be used for expectedness assessment and determining expedited reporting requirements. The events that do not require recording or reporting are listed below.

- Discomfort in foot or feet whilst wearing inserts
- Blisters or calluses
- Skin irritation
- Discomfort or muscle aches and pains in the legs e.g. as a result of altered gait
- New callus/corn formation
- Soft tissue musculoskeletal injury
- Tight shoes
- Feeling unstable whilst wearing inserts.
- Any elective or pre-planned treatment for a pre-existing condition, unrelated to the 1st MTPJ

Any event that is not listed above, or any event above that is considered untoward, excessive for insert use should be recorded by the treating clinical team, outcome assessors or study team, as appropriate. This will include events such as foot ulceration, foot infection requiring treatment, and/or falls. All AEs should be assessed to consider if they constitute a 'serious adverse event' below.

6.1.2 Serious adverse events

A Serious Adverse Event is an AE that fulfils one or more of following criteria:

- Results in death
- Is immediately life-threatening
- Requires hospitalisation or prolongation of existing hospitalisation
- Results in persistent or significant disability or incapacity
- Is a congenital abnormality or birth defect
- Is an important medical condition or immediate intervention was required to prevent one of the above.

Where participants are lost to follow-up, we will contact clinical teams to ask to document or record SAEs wherever possible e.g. from clinic records.

6.1.3 Assessing and reporting SAEs and related SAEs

All reportable **SAEs** occurring from the time of randomisation until one-year post-randomisation must be recorded on the SAE Form and emailed to WCTU (who will receive SAEs on behalf of the Sponsor), **within 24 hours** of the research staff becoming aware of the event. For each **SAE** the following information will be collected:

- full details in medical terms and case description
- event duration (start and end dates, if applicable)
- action taken
- outcome
- seriousness criteria
- causality (i.e. relatedness to intervention), in the opinion of the investigator
- whether the event would be considered expected or unexpected (to be assessed and added by a delegate of the Sponsor).

Any change of condition or other follow-up information should be sent to WCTU as soon as it is available. Events will be followed up until the event has resolved or a final outcome has been reached. An outcome of 'unknown' is not considered to be an acceptable final outcome. An outcome of 'not yet resolved' is an acceptable final outcome for non-serious AEs at the end of a patient's participation in a trial, and for SAEs at database lock.

SAEs, except for those listed as exemptions, will be reported using the SAE form. The PI or an appropriate delegate in each centre must report any SAEs to the trial coordinating centre within 24 hours of them becoming aware of the event. In the event that a clinical delegate of the PI is unable to assess causality within 24 hours, or is unavailable, any nominated person on the delegation log may send a partially completed SAE form. Further details should then be sent by site as soon as practically possible.

AEs or SAEs may be identified by the coordinating centre from the CRFs, either from specific questions or from answers within PROMs. If this occurs, the coordinating centre may query the site for details of the event either if it is unclear, or in the case of all SAEs (for the purposes of the sites own clinical governance). This will be determined on a case-by-case basis, and the potential to do so will be included in the participant information sheet (PIS).

The SAE form should be emailed to the study team: [contact] and WCTU QA team: [contact]. The TM will liaise with the investigator to compile all the necessary information. The trial coordinating centre is responsible for reporting any related and unexpected SAEs (i.e. events that are serious, related, and unexpected to the sponsor and REC within required timelines. Events which are possibly, probably or definitely related to the trial intervention and are unexpected **will be reported to the REC within 15 days**. To note, any adverse event which is serious and considered related to the insert would be unexpected and therefore reported to the REC.

The legal responsibility for reporting SAEs lies with the manufacturer or their authorised representative. However, the MHRA also has a voluntary reporting requirement for 'users' of devices i.e. where a device is being used in a trial in which the manufacturer has no involvement, and in this case, the coordinating centre would submit the appropriate reports and also inform the manufacturer of the event.

The causality of SAEs (i.e. relationship to trial treatment) will be assessed by the investigator(s) on the SAE form using the following descriptions:

Table 3: Definitions of Causality

Relationship	Description
to trial device	
Unrelated	There is no evidence of any causal relationship

Unlikely to be related	There is little evidence to suggest there is a causal relationship (e.g. the event did not occur within a reasonable time after administration of the trial intervention or device). There is another reasonable explanation for the event (e.g. the patient's clinical condition, other co- treatment).
Possible relationship	There is some evidence to suggest a causal relationship (e.g. because the event occurs within a reasonable time after administration of the trial intervention or device). However, the influence of other factors may have contributed to the event (e.g. the patient's clinical condition, other concomitant treatments).
Probable relationship	There is evidence to suggest a causal relationship and the influence of other factors is unlikely.
Definitely related	There is clear evidence to suggest a causal relationship and other possible contributing factors can be ruled out.

The following process will be used to review individual SAEs

• Clinical review (by a clinical TMG member) of a line listing of all life-threatening SAEs or SAEs resulting in death within one week of their occurrence.

The following process will be used to independently monitor trends in SAEs in addition to usual trial safety monitoring procedures.

• Cumulative review of all safety information by the DMC on a regular basis.

A member of the Principal Investigator's trial team will be instructed to closely monitor each participant who experiences an AE until the outcome of the AE has been determined.

6.2 Responsibilities

Principal Investigator (PI) or Delegate:

- Checking for AEs when participants attend for treatment / follow-up.
- Using medical judgement in assigning seriousness and causality.
- Ensuring that all SAEs are recorded and reported to the Sponsor within 24 hours of becoming aware of the event and provide further follow-up information as soon as available. Ensuring that SAEs are chased with Sponsor if a record of receipt is not received within two working days of initial reporting.
- Ensuring that AEs are recorded in line with the requirements of the protocol.

Chief Investigator (CI) / delegate or independent clinical reviewer:

- Clinical oversight of the safety of patients participating in the trial, including an ongoing review of the risk/benefit.
- Using medical judgement in assigning causality.
- Assessment of expectedness

- Immediate review of all related and unexpected SAEs
- Review of AEs/SAEs in accordance with the trial risk assessment and protocol as detailed in the Trial Monitoring Plan.

Sponsor (University of Warwick):

- All AEs (which meet the criteria in 6.1.1) will be recorded in the CRF
- Central data collection and verification of AEs, and SAEs, according to the trial protocol.
- Reporting safety information to the CI, delegate or independent clinical reviewer for the ongoing assessment of the risk/benefit according to the Trial Monitoring Plan.
- Reporting safety information to the independent oversight committees identified for the trial (Data Monitoring Committee (DMC) and/or Trial Steering Committee (TSC)) according to the Trial Monitoring Plan.
- Expedited reporting of related and unexpected SAEs to the REC within required timelines.
- Notifying Investigators of related and unexpected SAEs that occur within the trial.
- The unblinding of a participant for the purpose of expedited reporting, only where strictly necessary.

TSC

• In accordance with the Trial Terms of Reference for the TSC, periodically reviewing safety data and liaising with the DMC regarding safety issues.

DMC

• In accordance with the Trial Terms of Reference for the DMC, periodically reviewing unblinded overall safety data to determine patterns and trends of events, or to identify safety issues, which would not be apparent on an individual case basis.

